2. SUMMARY

| | |
|----------------------------------------------|----------------------------------------------------------------------------------------------------------------------------------------------------------------------------------------------------------------------------------------------------------------------------------------------------------------------------------------------------------------------------------------------------------------------------------------------------------------------------------------------------------------------------------------------------------------------------------------------------------------------------------------------------------------------------------------------------------------------------------------------|
| Study Objective | To compare the 1-, 3-, and 5-year outcomes of a second aqueous shunt (SAS) to Transscleral Diode Laser Cyclophotocoagulation (TLC) in eyes with uncontrolled glaucoma with a single existing aqueous tube shunt implant. |
| Study Endpoint (Failure) | 
 1. Intraocular pressure (IOP) 
 a. > 18 mmHg on maximum tolerated topical IOP-lowering medications, or b. reduced by < 20% on maximum tolerated topical IOP-lowering medications from medicated preoperative IOP, or c. ≤ 5 mmHg without glaucoma medications on IOP confirmation visit(s), 6 months after initial study intervention; or 2. Additional reoperation for glaucoma (enhancement procedures allowed in the first 4 months); or 3. Addition of an oral carbonic anhydrase inhibitor (CAI) for the study eye on or after the 6-month visit; or 4. No light perception (NLP) |
| Study Population | 18 to 85 years of age with uncontrolled glaucoma on maximum tolerated topical therapy with a single existing tube shunt implant |
| Study Design | Prospective, multicenter, randomized, masked, parallel group |
| Treatment Groups | 
 1. Second Aqueous Shunt Implant (SAS) 2. Transscleral Diode Laser Cyclophotocoagulation (TLC) |
| Duration of Participant Participation | 5 Years |
| Number of Study Visits | 10 – 13 visits |
| # of Evaluable Participants | 91 in each group (182 total) |
| Anticipated Maximum # of Participants | 280, allowing for a 35% dropout |
| Recruitment Period | 1 year |
| Study Centers | Up to 70 centers |
| Site Funding Available | No |
| IRB Submission | Site's responsibility (submission, questions, fees) |

3. BACKGROUND INFORMATION

Aqueous shunts (AS) are commonly used to treat eyes with glaucoma refractory to medical therapy or eyes that have failed or are at high risk of failing a filtering procedure. The Tube Versus Trabeculectomy (TVT) Study demonstrated that AS were more effective in the long term (5 years) than trabeculectomy in eyes with prior incisional surgery and uncontrolled glaucoma.² Largely due to the results of TVT, the frequency of AS implantation has increased 410% between 1994 and 2012.¹ Additionally, it led to the question being evaluated in the Primary Tube Versus Trabeculectomy (PTVT) Study whether primary AS surgery may be appropriate in treating uncontrolled primary open-angle glaucoma, which may further increase the rates of implantation. Despite the favorable results compared to trabeculectomy, approximately 30-50% of AS fail within the first 5 years of implantation.^{2, 3}

For eyes where an initial AS fails to control IOP and medical therapy is ineffective, two surgical techniques are often used -- implantation of a second AS or cyclodestruction. Regrettably, there is very little clinical evidence to direct care in cases of initial AS failure. Published studies investigating these two approaches separately conclude that both of these procedures are valid options for eyes with failed initial AS,⁴⁻¹¹ in that they are successful in lowering IOP. However, these studies are small and retrospective, with the exception of one small, non-comparative, prospective case series.¹²

Two retrospective studies published compared second AS with cyclodestruction after a failed initial AS: one with 17 eyes (8 AS, 9 cyclodestruction) in pediatric patients,¹³ and the other with 47 eyes (15 AS, 32 cyclodestruction) predominantly in adults.¹⁴ Both studies reported reduction of IOP and number of IOP-lowering medications in both treatment groups. The latter study showed that eyes treated with cyclodestruction had a higher early failure rate (mean 13.5 months), while the second AS group had few early failures, but a higher rate of long-term failures and complications (mean = 6.1 years).¹⁴ While these studies provide the best current clinical guidance for eyes that have failed an initial AS, there is no prospective, randomized, controlled clinical trial evaluating the efficacy or safety of these two treatment options, nor are there any data on the effects of these interventions in this setting on quality of life.

The goal of this study is to provide high-level evidence to guide clinical decision-making in the management of this increasing population of patients given the increasing rates of AS implantation.

4. TRIAL OBJECTIVES

4.1. Primary Aim:

The primary aim is to compare short- (1 year), mid- (3 years), and long-term (5 years) cumulative incidences of failures in participants who undergo a second aqueous shunt (SAS) to those cumulative incidences of failures in participants who undergo transscleral diode laser cyclophotocoagulation (TLC) for eyes with uncontrolled glaucoma with a single existing aqueous tube shunt implant.

The primary outcome variable is success or failure of treatment at 1, 3, and 5 years, where treatment failure is defined as meeting one or more of the following 4 criteria:

1. Intraocular pressure (IOP)
 - a) >18 mm Hg on maximum tolerated topical IOP-lowering medications, or
 - b) Reduction of < 20% IOP on maximum tolerated topical IOP-lowering medications from medicated preoperative IOP, or
 - c) \leq 5 mm Hg without IOP-lowering medicationson IOP confirmation visit, 6 months after initial study intervention; or
2. Reoperation for glaucoma; or
3. Addition of an oral CAI for the study eye on or after the 6-Month Study Visit; or
4. Loss of light perception vision (NLP).

4.2. Secondary Aims

The secondary aims are to compare safety (i.e. complications, loss of best-corrected visual acuity [BCVA], and pain) and vision-related quality of life between the two treatments, including:

1. Cumulative incidence of vision-threatening complications at 1, 3, and 5 years after initial study intervention;
2. BCVA at scheduled visits after the 6-month postoperative visit. Changes of BCVA from baseline and the incidence of eyes that have lost more than 2 lines of BCVA will be compared between groups at each visit.
3. Incidence and severity of pain at the 1-week and 1-month postoperative visits.
4. Total number of visits during the first 3 months, first year, and over 5 years.
5. Changes in vision-related quality of life from baseline to 1-, 3-, and 5-year visits, assessed by the NEI VFQ-25.

5. TRIAL DESIGN

This proposed study is a prospective, randomized, multicenter, masked, parallel group study. Sites will be selected based on surgeon's surgical qualifications and experience with the two study interventions, as well as on sufficient staffing and facility resources for conducting the study examinations. The participants will be randomly assigned to receive a SAS or undergo TLC. The cumulative incidences of treatment failure at 1, 3 and 5 years will be compared between groups.

6. PARTICIPANTS

All patients who meet the following eligibility criteria may be enrolled.

6.1. Inclusion Criteria

Patients who meet the following inclusion criteria may be enrolled:

1. Women and men 18 to 85 years of age
2. Glaucoma not adequately controlled (IOP > 18 mmHg on maximum tolerated topical therapy) with a single existing aqueous tube shunt (AS). *If the participant is taking oral carbonic anhydrase inhibitors (CAI) at the time of screening, the IOP prior to initiation of an oral CAI may be used*
3. Best-corrected visual acuity (BCVA) of hand motion (HM) or better in the study eye

6.2. Exclusion Criteria

Patients who meet the following exclusion criteria may NOT be enrolled:

1. Monocular
2. Presence of more than one AS *in the study eye*
3. Previous cyclodestruction *in the study eye*
4. Presence of active iris neovascularization *in the study eye*
5. Binocular diplopia
6. Presence of scleral buckle *in the study eye*
7. History of scleritis in either eye
8. History of scleromalacia *in the study eye*
9. Insufficient conjunctiva to cover AS in the *study eye*
10. IOP cannot be accurately measured with Goldmann applanation, Pneumotonometer, or Tono-Pen *in the study eye* (e.g. keratoprosthesis)

11. Presence of silicone oil *in the study eye*
12. Presence of retinal detachment *in the study eye*
13. Presence of intraocular or orbital tumor affecting *the study eye*
14. Need for cataract extraction or concurrent procedure at the time of study treatment, except tectonic aqueous shunt revisions for both groups is allowed
15. In the opinion of the investigator, should not be enrolled in this study (e.g. uncontrolled systemic diseases, altered mental status, etc.)
16. Unwilling or unable to give consent and satisfy requirements of the study (e.g. accept randomization, follow-up for 5 years, etc.)

6.3. Eye

If both eyes of a participant are eligible *and* the investigator plans to perform either of the study procedures in both eyes within three months of screening, the first eye to be treated will be the study eye.

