7.2. Randomization Scheme

An adaptive block randomization scheme will be implemented with a block size of 4 and balancing between NVG and non-NVG strata within each site.

Upon completion of the Screening/Baseline visit, the study eye will be randomly assigned to one of the 2 treatment groups: SAS or TLC within each stratum (NVG vs non-NVG) and each site based on the computer generated assignment.

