10.2. Scheduled Assessments

Table 2 outlines the schedule of assessments at each visit throughout the study period. Data from the study visits must be entered into the REDCap system within 5 business days of the exam.

Table 2: Schedule of Assessments

| Assessment | Screening / Baseline | Surgery – Day 0 | Week 1 | Month 1 | Month 3 | Enhancement Procedure | Enhancement Month 1 | Month 6 | Month 12 | Year 2 | Year 3 | Year 5 / Exit | Confirmation Visit*** |
|------------------------------------|----------------------|-----------------|--------|---------|---------|-----------------------|---------------------|---------|----------|--------|--------|---------------|-----------------------|
| Informed Consent | X | | | | | | | | | | | | |
| Demographics | X | | | | | | | | | | | | |
| Medical / Ophthalmic History | X | | | | | | | | | | | | |
| Historical VF MD* | SE | | | | | | | | | | | | |
| Concomitant Medications | OU | | OU | OU | OU | OU | OU | OU | OU | OU | OU | OU | OU |
| Inclusion/Exclusion Criteria | X | | | | | | | | | | | | |
| Visual Acuity | OU | | SE | SE | SE | | SE | SE | SE | SE | SE | SE | |
| Binocular Diplopia | X | | | | X | | | X | X | X | X | X | |
| External Ocular Examination | OU | | | OU | OU | | | | OU | | | | |
| Specular Microscopy (CCT and CD)** | SE | | | | | | | | SE | | | SE | |
| Biomicroscopy | SE | | SE | SE | SE | | SE | SE | SE | SE | SE | SE | |
| Intraocular Pressure | OU | | SE | SE | SE | | SE | SE | SE | SE | SE | SE | SE |
| Ultrasonic Pachymetry | OU | | | | | | | | SE | | | SE | |
| Ophthalmoscopy | SE | | | | | | | | SE | | | SE | |
| OCT (macula) | SE | | | | | | | | SE | | | | |
| Procedure | | SE | | | | SE | | | | | | | |
| VFQ-25 | X | | | | | | | | X | | X | X | |
| Randomization | X | | | | | | | | | | | | |
| Pain Scale | | | X | X | | | | | | | | | |
| Adverse Events | X | X | X | X | X | X | X | X | X | X | X | X | X |

Perform assessment, not eye specific (X), study eye only (SE), both eyes (OU)

* The mean deviation from the participants last visual field (if available) prior to enrollment will be recorded to further describe the stage of disease in the study population.

**Specular microscopy (SM) will be performed at sites where SM is available

***Confirmation visits will occur prior to the conduct of any surgical intervention in the study eye when IOP is believed to have met endpoint (failure).

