10.3.11. Universal Pain Scale

Following the initial study treatment, participant pain or discomfort will be assessed at Week 1 and Month 1 visits with the Universal Pain Scale (Appendix 1).

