16.3.3. To compare BCVA at visits after the 6-month postoperative visit

Snellen BCVA will be converted to line scale by logMAR. Differences between study groups will be analyzed both cross-sectionally and longitudinally. Either a Student's t-test or a nonparametric Wilcoxon rank sum test will be used for the cross-sectional comparison between groups and a mixed-effect model with repeated measurements will be used to compare two groups over the study period.

The incidence of loss more than 2 lines from baseline to each follow-up visit will be compared with a Fisher exact test.

16.3.4. To compare incidence and severity of pain between groups at the initial 1-week and 1-month postoperative visits.

The incidence and severity of pain at the 1-week and 1-month follow-up visits will be compared with a Fisher exact test and a Student t test (or a Wilcoxon rank sum test), respectively.

16.3.5. To compare the total number of visits during the first three months, during the first year, and during all five years of the study between groups.

[figure not shown]
Differences between study groups in total number of visits during the first three months, during the first year, and during all five years of the study will be compared between study groups on the distributions with either a Student's t-test or a Wilcoxon rank sum test.

The large number of measures used to assess safety and the frequency of interim analyses to monitor safety introduce the problem of multiple comparisons, i.e. some comparisons are statistically significant because of the large number of statistical tests conducted. Analyses that adjust for multiple comparisons will be conducted and both adjusted and unadjusted multiple comparisons will be reported to the Data and Safety Monitoring Committee.

REFERENCES

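### Pain is scored per person although some participants will have both eyes operated, so pain from an unrandomised fellow-eye procedure can enter the arm comparison, mainly at Month 1

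*Combined protocol and SAP*

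**What the plan says.** Section 6.3 applies when both eyes are eligible and "the investigator plans to perform either of the study procedures in both eyes within three months of screening". It settles one thing: "the first eye to be treated will be the study eye". The second operation therefore does not precede the first, and it comes during follow-up unless both are done together.

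Section 7.2 randomises one eye per person: "the study eye will be randomly assigned to one of the 2 treatment groups". None of the 16 criteria in Section 6.2 excludes planned fellow-eye surgery. No section fixes the type or timing of the fellow-eye procedure, or accounts for it in the analysis.

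The legend of Table 2 (Section 10.2) reads "Perform assessment, not eye specific (X), study eye only (SE), both eyes (OU". The Pain Scale carries an X at Week 1 and Month 1. Section 10.3.11 agrees with that coding: "participant pain or discomfort will be assessed at Week 1 and Month 1 visits with the Universal Pain Scale". Section 16.3.4 compares pain incidence with a Fisher exact test and severity with a t-test or rank-sum test, without covariates.

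The VFQ-25 is also coded X. Visits are compared as totals, with no eye attached (Section 16.3.5: "Differences between study groups in total number of visits during the first three months"). By contrast, follow-up IOP and visual acuity are coded for the study eye, and the oral CAI failure criterion is worded for the study eye.

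**The concern.** Secondary aim 3 is meant to compare the pain of a second shunt with the pain of cyclophotocoagulation. In a participant who has both eyes operated before the Month 1 visit, a person-level pain score reflects the randomised procedure plus a second procedure that was not randomised.

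The masking in Sections 7.3 and 10.3.7 concerns the IOP reader. The surgeon knows the assignment and may choose the type and timing of the fellow-eye procedure after seeing how the study eye does. The plan for bilateral surgery is made before randomisation, but what is actually done comes after it. If the two arms then differ in fellow-eye surgery, the pain comparison no longer isolates the randomised treatment.

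**Working it through.** **The plan's own figure.** The documents give no planning figure for pain, visits or the bilateral share. The only sample size is for the primary outcome (Section 7.4: 50% vs 30%, alpha 5%, power 80%). The unpooled two-proportion formula, two-sided, gives (1.960 + 0.842)² × (0.50×0.50 + 0.30×0.70) / 0.20² = 90.3, so 91 per group. For dropout, 182 / 0.65 = 280. Both figures reproduce, and this point does not affect either.

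**Timing.** Inputs:
- study eye treated within 45 days of screening (Section 8.1);
- both eyes planned within three months, about 91 days (Section 6.3);
- Week 1 window days 4-21; Month 1 window days 22-59, preferred days 23-37 (Table 1).

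If the study eye is treated *d* days after screening, the planned limit for the fellow eye is study day 91 − *d*: day 91 for *d* = 0 and day 46 for *d* = 45.
- Week 1 pain is affected only if the second operation follows within days, at most three weeks.
- Month 1 pain is affected if the second operation precedes that visit. An operation on day 46 comes after a visit held in the preferred window, and matters only for a visit held on days 46-59.
- An operation near day 91 misses both pain visits but falls at about the end of the first-three-months visit count.

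Overlap with Month 1 is therefore possible, but not certain.

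**Size for pain.** All of the following are assumptions, not figures from the documents: 140 per arm (280/2), bilateral share *b* of 5-30%, and fellow-eye pain (probability *q*) independent of study-eye pain (probability *p*). Observed incidence in an arm is

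p + b × q × (1 − p).

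| Scenario | Difference, b = 5% to 30% | Power |
|---|---|---|
| No true difference (30% vs 30%), same fellow-eye surgery in both arms | 0 (both arms rise to 31.1-36.3%) | – |
| No true difference, fellow-eye surgery in one arm only (extreme) | false 1.1 to 6.3 points | – |
| True 40% vs 25%, same fellow-eye mix in both arms (q = 32.5%) | 14.8 to 13.5 points | 75% to 64% |
| True 40% vs 25%, fellow eye gets the opposite procedure | 14.3 to 10.5 points | 72% to 44% |
| True 40% vs 25%, fellow eye gets the same procedure | 15.3 to 16.6 points | 78% to 82% |

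Without fellow-eye surgery the true difference is 15.0 points and power is 77%. Examples at b = 30%:
- one arm only: 0.30 × 0.30 × 0.70 = 0.063;
- same mix: (0.40 + 0.30×0.325×0.60) − (0.25 + 0.30×0.325×0.75) = 0.4585 − 0.3231 = 0.1354.

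**Size for visits.** With an assumed 2-4 extra visits per fellow-eye operation, each arm's mean rises by 0.05 × 2 = 0.1 to 0.30 × 4 = 1.2 visits. If the share is equal in both arms, the difference moves only by *b* times the between-arm difference in fellow-eye visits. For a difference of one visit that is 0.05-0.30 visits.

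**The case against.** A reader might infer that fellow-eye surgery is simply credited to the study treatment. The documents do not support that. The bilateral plan exists at screening and assignment follows, so randomisation balances the plan in expectation. Equal fellow-eye surgery in both arms leaves a null difference at zero. Bias requires that what is done to the fellow eye depends on the arm, and nothing in the documents shows that it does. This objection stands and limits the point.

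Three other strong readings also fail.
- *The two sources cannot be separated afterwards.* The Procedure row in Table 2 is for the study eye, but concomitant medications are recorded for both eyes and all adverse events are reported. The case report forms are not in the documents, so fellow-eye surgery may be captured there.
- *Visit counts and VFQ-25 are wrong because they are per person.* Total visits can legitimately mean participant burden, and the VFQ-25 asks about eyesight with both eyes. If the assignment changes when the other eye is treated, the resulting visits are arguably a consequence of assignment. Asking site staff to attribute each visit to an eye could itself introduce bias.
- *The distortion is large.* Eligible bilateral participants need a single existing shunt and uncontrolled IOP in each eye, plus a plan for both within three months. The share may be small.

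The pain scale itself (Appendix 1) is not shown, so wording there that names the study eye cannot be ruled out. The coding in Table 2 and the text of Section 10.3.11 nevertheless point to a person-level question, and no section says otherwise.

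**Conclusion.** The point holds in a limited form. The protocol accepts participants planned for surgery in both eyes, randomises one eye, and describes pain as a person-level measure. Fellow-eye pain can therefore enter secondary aim 3, mainly at Month 1. With similar fellow-eye surgery in both arms the result is noise or dilution: at assumed bilateral shares of 5-30%, about 0.2 to 1.5 points off a true 15-point difference when the fellow-eye mix is the same. Bias arises only if frequency, timing or type depends on the assignment. That is possible, because the surgeon knows the assignment and no section fixes the fellow-eye procedure. Its assumed extreme is 1.1-6.3 points.

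These sizes rest on assumed pain rates, independence between eyes and a bilateral share that the documents do not give. The primary outcome and the sample size are untouched. Severity is minor.

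**What to change.** 1. In Section 10.3.11 and Table 2, ask the pain scale for the study eye and code it SE.
2. Record at screening, before randomisation, whether surgery in both eyes is planned. During follow-up, record the date and type of any fellow-eye glaucoma procedure.
3. Keep total visits and VFQ-25 as person-level outcomes. In Sections 16.3.1, 16.3.4 and 16.3.5, add a sensitivity analysis that repeats the VFQ-25, pain and visit comparisons without participants planned at screening for bilateral surgery. That group is fixed before assignment, so leaving it out preserves the randomised comparison. Excluding people by the fellow-eye surgery they actually received would not.

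Cost: minor changes to form wording, three fields (plan, date, type) and one sensitivity run. No visit is added.

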7. STUDY DESIGN CONSIDERATIONS

7.1. Stratification

Eyes will be classified into neovascular glaucoma (NVG) or non-NVG group based on glaucoma diagnosis for the purposes of generalizability.

7.2. Randomization Scheme

An adaptive block randomization scheme will be implemented with a block size of 4 and balancing between NVG and non-NVG strata within each site.

Upon completion of the Screening/Baseline visit, the study eye will be randomly assigned to one of the 2 treatment groups: SAS or TLC within each stratum (NVG vs non-NVG) and each site based on the computer generated assignment.

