7.5. Recruitment period

The intent of this study is to answer a question that is desperately needed within the glaucoma community. In order to have the question answered in a timely manner, the study plans to involve as many sites as possible from the AGS membership and thereby shorten the recruitment period to one year.

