8. RECRUITMENT PROCEDURE

Recruitment is open for competitive enrollment. The Investigators and/or study staff will enroll qualified participants into the study. After reviewing and signing the informed consent form, a study number will be assigned to the participant in a sequential manner by site identification (assigned by REDCap) followed by participant number. All potential participants will undergo an initial screening examination (Table 2) in order to determine study eligibility.

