16. DATA ANALYSIS

16.1. *Interim Analysis/Safety Monitoring*

A number of interim analyses will be performed. The purpose of these analyses will be:

- a. To monitor recruitment targets in subgroups of interest (NVG vs non-NVG) and to monitor balance between treatment groups with regard to prognostic factors.
- b. To provide a regular mechanism for evaluating data quality, protocol adherence, and side-effect patterns including adverse reactions.
- c. To determine whether the study should be terminated early. Negative results could suggest that there is no possibility of ever establishing significance between-group differences.
- d. To assess the possibility that a positive but nonsignificant trend might require an increase in the originally projected sample size or an increase in the study duration.

Interim analyses will be performed every 3 months for the first year of enrollment and every 6 months thereafter. Interim analyses may also be performed at any time upon the request of the DSMB. The DCC will provide the results to the DSMB for making all decisions regarding the future conduct of the study. All investigators will be masked as to the results of interim analyses.

16.2. *Primary Analysis*

In the primary analysis, the null hypothesis is that there is no difference in one-year cumulative failure rates between the SAS group and the TLC group. The cumulative failure rates will be compared with Fisher exact test with one degree of freedom. The survival time from the treatment to failure will be estimated by Kaplan-Meier survival curve for each group and compared between the two treatment groups with the log-rank test. The potential effect of covariates will be assessed with the Cox proportional hazards models.

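### With close to 70 sites and an NVG share of about 20% or less (not stated), blocks of 4 within site-by-NVG cells leave trial-wide NVG balance only modestly better than chance

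*Combined protocol and SAP*

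**What the plan says.** Section 7.2 sets the scheme: "An adaptive block randomization scheme will be implemented with a block size of 4 and balancing between NVG and non-NVG strata within each site". It then says that the study eye is assigned to "SAS or TLC within each stratum (NVG vs non-NVG) and each site based on the computer generated assignment". Each site therefore has two lists. *Adaptive* is not defined.

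The Summary gives the scale, "Up to 70 centers" and an anticipated maximum of "280, allowing for a 35% dropout". Section 7.5 says that "the study plans to involve as many sites as possible from the AGS membership and thereby shorten the recruitment period to one year". Section 8 adds "Recruitment is open for competitive enrollment", and no minimum per site is given.

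Section 7.1 gives the reason for the NVG classification: "Eyes will be classified into neovascular glaucoma (NVG) or non-NVG group based on glaucoma diagnosis for the purposes of generalizability". Section 16.1 calls NVG versus non-NVG a subgroup of interest and uses the interim looks "to monitor balance between treatment groups with regard to prognostic factors". In Section 16.2 the Fisher exact and log-rank tests are not described as stratified. Covariates, none of them named, are assessed in Cox models. The expected NVG share appears nowhere. Section 6.2 excludes active iris neovascularization, which suggests a small NVG stratum.

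**The concern.** A permuted block forces equal arms only when it is filled. If a site contributes about one NVG eye, that eye takes the first place in a fresh block, and its arm is a coin toss. Added over many sites, such eyes give a trial-wide NVG split not much tighter than simple randomisation would give.

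NVG is the only clinical factor used in allocation. Neither test in Section 16.2 is committed to adjusting for it, so a chance imbalance in NVG would show in the unadjusted comparison. Interim monitoring can reveal an uneven split but cannot undo it.

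**Working it through.** **The plan's own figures.** With 50% vs 30% failure, two-sided 5% alpha and 80% power, n per arm = (1.960 + 0.842)² × (0.50×0.50 + 0.30×0.70) / 0.20² = 90.26, rounded up to 91. Then 182 / 0.65 = 280. Both match Section 7.4. The plan gives no figure for the number of lists or the expected balance.

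**Lists.** 70 sites × 2 strata = 140 lists at most; 280 / 140 = 2 participants per list on average, against a block of 4.

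**Imbalance left by one block.** For k eyes in a block of 4, the variance of (SAS minus TLC) is 1, 4/3, 1, 0 for k = 1, 2, 3, 4. A coin toss gives 1, 2, 3, 4.

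**70 sites of exactly 4, NVG share 20% (assumption).** The NVG count per site is binomial(4, 0.2), with probabilities 0.4096, 0.1536, 0.0256 and 0.0016 for k = 1 to 4.

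- Per site: 0.4096×1 + 0.1536×4/3 + 0.0256×1 = 0.64.
- Trial: 70 × 0.64 = 44.8, so the SD is 6.7 eyes.
- Coin toss: 280 × 0.2 = 56 NVG eyes, √56 = 7.5.
- One central list in blocks of 4: the last block is equally likely to hold 1, 2, 3 or 4 eyes, so the variance is (1 + 4/3 + 1 + 0)/4 = 0.83 and the SD is 0.9.

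**Sensitivity to site number and size.** Simulation at 20% NVG and 280 participants, plain permuted blocks of 4. Uneven sites use gamma weights with shape 1 (assumption).

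| Sites | Sizes | SD of NVG arm difference | NVG eyes in unfilled blocks | Chance of 33 vs 23 or worse |
|---|---|---|---|---|
| 70 | 4 each | 6.7 | 99% | 15% |
| 70 | uneven | 5.7 | 80% | 9% |
| 40 | 7 each | 5.8 | 90% | 10% |
| 40 | uneven | 4.9 | 63% | 5% |
| 20 | 14 each | 4.2 | 56% | 2% |
| 20 | uneven | 3.7 | 41% | 1% |
| any | coin toss | 7.5 | n/a | 20% |
| any | central NVG list | 0.9 | at most the last block | 0 |

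At 70 sites (uneven to equal), the SD is 4.6 to 5.0 against 5.3 by coin toss at 10% NVG, and 6.2 to 7.7 against 9.2 at 30%.

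**Effect on the arm difference.** A 33 vs 23 split among 140 per arm is a 10/140 = 7.1-point difference in NVG share. If NVG eyes fail 30 points more often (assumption), the arm difference moves by 0.071 × 30 = 2.1 points; at a 20-point gap, by 1.4 points. The design difference is 20 points at 5 years.

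**Variance at stake.** The between-stratum share is p(1−p) × gap² / 0.24, where 0.24 = 0.40 × 0.60 uses the mean of the two 5-year design rates. With p = 0.2: 0.16 × 0.04 / 0.24 = 2.7% (20-point gap) and 0.16 × 0.09 / 0.24 = 6.0% (30-point gap). For a test that uses it, the design value 2.80 becomes 2.80/√0.973 = 2.84 or 2.80/√0.94 = 2.89, so power goes from 80% to about 81-82%.

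**Within-site balance under a central NVG list.** The root-mean-square arm difference per site goes from 1.13 to about 1.2 with 70 sites of 4, and from 1.29 to about 1.9 with 20 sites of 14.

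**The case against.** A reader might infer that almost no NVG block ever fills and that the scheme does no better than a coin toss. The documents do not support that without conditions. Seventy is a ceiling, the NVG share is not given, and competitive enrollment makes uneven sites likely. Partial blocks also help: two eyes in a block have variance 4/3 rather than 2, and three have 1 rather than 3. At 20 sites the SD is about 4, against 7.5 by coin toss.

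If *adaptive* means that allocation responds to running balance across sites, the permuted-block calculation does not apply at all. The wording about sites points the other way, but the term is undefined.

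A reader might also infer that the primary comparison is biased. It is not. Randomisation is valid, and the error rates of the Fisher and log-rank tests already allow for chance covariate imbalance. The sample size is unaffected. Stratifying by site is a defensible choice when surgeons differ, Section 7.1 gives generalizability as the purpose of the NVG classification, and the Cox models could include NVG.

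These points limit the claim and its weight. What stands is that, in every case checked from 20 to 70 sites and 10% to 30% NVG, the planned scheme leaves an NVG imbalance at least 3.7 times that of a central list (smallest ratio 3.4/0.91). Section 7.1's purpose would be served by recording the diagnosis; it does not require balancing NVG inside each site.

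**Conclusion.** The concern holds conditionally. It needs a site count near 70, an NVG share of about 20% or less, and no cross-site balancing under *adaptive*. The documents settle none of these three. The shortfall in balance is then real but moderate: the SD of the NVG arm difference is about 10% to 25% below that of a coin toss at 20% NVG. With 20 to 40 sites, the scheme does clearly better than chance.

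The consequence is small: a shift of about 1 to 2 points in the arm difference after a 33 vs 23 split, and 3-6% of variance, both resting on an assumed failure gap of 20-30 points. A central list alone would not bring that gain into an unadjusted test; the analysis must also use NVG. This is a cheap improvement to the design, not the correction of an invalid one.

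**What to change.** In Section 7.2:

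- Define *adaptive* and state the expected NVG share and number of enrolling sites.
- Assign NVG eyes from one central list across all sites, and keep the non-NVG lists by site. Minimisation on trial-wide NVG and on site, with a random element, is an alternative.

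In Section 16.2, stratify the primary comparison by NVG, for example with a Cochran-Mantel-Haenszel test for the cumulative failure rates and a stratified log-rank test for time to failure. This step carries the precision into the test. It would recover most of it even without the central list, since a 33 vs 23 split keeps 4×33×23/56² = 97% of the information in the NVG stratum. It is also the part that can still be adopted if randomisation has begun.

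The cost is a new allocation table in REDCap before enrollment and a few lines in Section 16.2, with no extra participants or data. The downside is that NVG eyes are no longer balanced within a site. That is negligible near 70 sites but noticeable if only about 20 enrol, so the choice should follow the realistic site count.
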